16. ADVERSE EVENTS

16.1. Departure from the Protocol for Individual Patients

When an emergency occurs requiring a departure from the protocol for a patient, departure will be only for that patient. In such circumstances, the investigator or other physician in attendance will contact the Medical Monitor or the Sponsor by telephone and follow up with a written description as soon as possible. The overseeing IRB should also be notified.

16.2. Definitions

An adverse event (AE) is defined as any untoward medical occurrence in a patient administered a medicinal product and which does not necessarily have to have a causal relationship with this treatment. An adverse event can therefore be any unfavorable and unintended sign, symptom, or disease temporally associated with the use of a medicinal product, whether or not considered related to this medicinal product.

A serious adverse event (SAE) is an adverse event that results in any of the following outcomes:

- Death
- Life-threatening event (i.e., the patient was, in the opinion of the investigator, at immediate risk of death from the event as it occurred. It does not include an event that, had it occurred in a more severe form, might have caused death
- Requires in-patient hospitalization or prolongs hospitalization
- A persistent or significant disability/incapacity or substantial disruption of the ability to conduct normal life functions
- Congenital anomaly/birth defect
- Other adverse events that may be considered serious based upon appropriate medical judgment, may jeopardize the patient and may require medical or surgical intervention to prevent one of the outcomes listed above.

Immediately Reportable Adverse Events (IRAE) is any serious AE or any AE that necessitates discontinuation of study product, including pregnancy.

Unexpected Adverse Event is any adverse drug experience, the specificity or severity of which is not consistent with the current approved product labeling (package insert) for the study product, the Investigator's Brochure, or as described in the clinical protocol and consent materials.

Intensity of Adverse Events are the maximum intensity of an AE during a day should be recorded on the eCRF. If the intensity of an AE changes over a number of days, then separate entries should be made having distinct onset dates for the changes in severity.

- Mild - AEs are usually transient, requiring no special treatment, and do not interfere with patient's daily activities.
- Moderate - AEs typically introduce a low level of inconvenience or concern to the patient and may interfere with daily activities but are usually ameliorated by simple therapeutic measures.
- Severe - AEs interrupt a patient's usual daily activity and traditionally require systemic drug therapy or other treatment.

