8.9.2 Adverse Events

AEs from 54-01/02 will be included in the analysis for 54-07. All AEs that were reported as ongoing in 54-01/02 will be added into the CRF for 54-07, while AEs reported as recovered/resolved will be pulled forward programmatically into 54-07.

AEs occurring during the study will be recorded and classified on the basis of MedDRA terminology. Descriptions of AEs will include the date of onset, the date the AE ended, the severity of the AE, the relationship to study product, the action taken regarding study product usage, the action taken to treat the AE, and the outcome. All reported treatment-emergent AEs (TEAEs) will be summarized by the number of patients reporting AEs, system organ class, severity, seriousness, and relationship to study product. TEAEs are those AEs with an onset on or after the date of the first study product application. For AEs recorded in the 54-07 study if the AE is not indicated as prior to first application on the CRF then it will be considered a TEAE. AEs from 54-01/02 for subjects who received S5G4T-1 in 54-01 or 54-02 will be considered a TEAE if they were considered at TEAE in the 54-01/02 study. AEs (including ongoing) from 54-01/02 study for subjects who received vehicle in 54-01 or 54-02 will be considered pre-treatment.

AEs will be summarized by period (and total) and by severity. Each patient will be counted only once within a SOC or a Preferred Term by using the AEs with the highest severity within each category.

AEs will be summarized by period (and total) and by relationship to study product. Each patient will be counted only once within a system organ class or a preferred term by using the AEs with the greatest relationship within each category.

If relationship to study drug is reported as definitely, probably, or possible, then this is defined as related. If relationship to study drug is reported as unlikely or not related, then this is defined as unrelated.

TEAEs will be summarized in total as well as by the following periods based on time of onset in relation to date of first application of S5G4T-1, based on the definitions below. Start dates will be imputed as described in Section 8.1.5.2.

- 0-12 Weeks $0 \leq \text{onset day} \leq 85$
- >12-28 Weeks $86 \leq \text{onset day} \leq 197$
- >28-52 Weeks $198 \leq \text{onset day} \leq 365$
- >52 Weeks $\text{onset day} \geq 366$

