1 – Mild	xx (xx.x%)		xx (xx.x%)
2 – Moderate	xx (xx.x%)		xx (xx.x%)
3 – Severe	xx (xx.x%)		xx (xx.x%)

^a Baseline is defined as the baseline value from SGT-54-01/SGT-54-02.

^b Table summaries based analysis visits, representing time from first dose of E-BPO 5% Cream.

SOURCE: USERNAME\SPONSOR\PROJECT\JOBNAME (DATE,TIME)

Table 14.3.1.1: Summary of Cutaneous Safety and Tolerability Evaluations
(Safety Population)
(Page 5 of 20)

	SGT-54-01/SGT-54-02 Vehicle Cream (N=xxx)	SGT-54-01/SG-54-02 E-BPO 5% Cream (N=xxx)	SGT-54-07 E-BPO 5% Cream (N=xxx)
Dryness			
Week 48 ^b			
n	xx	NA	xx
0 – None	xx (xx.x%)		xx (xx.x%)
1 – Mild	xx (xx.x%)		xx (xx.x%)
2 – Moderate	xx (xx.x%)		xx (xx.x%)
3 – Severe	xx (xx.x%)		xx (xx.x%)
Week 52 ^b			
n	xx	NA	xx
0 – None	xx (xx.x%)		xx (xx.x%)
1 – Mild	xx (xx.x%)		xx (xx.x%)
2 – Moderate	xx (xx.x%)		xx (xx.x%)
3 – Severe	xx (xx.x%)		xx (xx.x%)

^a Baseline is defined as the baseline value from SGT-54-01/SGT-54-02.

^b Table summaries based analysis visits, representing time from first dose of E-BPO 5% Cream.

SOURCE: USERNAME\SPONSOR\PROJECT\JOBNAME (DATE,TIME)

Repeat these pages for [Scaling, Itching and Burning/Stinging]

Table 14.3.1.2.1: Summary of Treatment-Emergent Adverse Event Characteristics
 (Safety Population)
 (Page 1 of 2)

	E-BPO 5% Cream (N=xxx)	
Subjects Reporting Any Treatment-Emergent Adverse Event	xx	(xx.x%)
Number of Treatment-Emergent Adverse Events	xx	
Subjects Reporting Any Serious Treatment-Emergent Adverse Event	xx	(xx.x%)
Number of Serious Treatment-Emergent Adverse Events	xx	
Subjects Reporting Treatment-Emergent Adverse Event with Outcome of Fatal	xx	(xx.x%)
Number of Treatment-Emergent Adverse Events with Outcome of Fatal	xx	
Subjects Who Discontinued Study Drug Due to a Treatment-Emergent Adverse Event	xx	(xx.x%)
Number of Treatment-Emergent Adverse Events Leading to Discontinuation of Study Drug	xx	
Subjects Who Discontinued from the Study Due to a Treatment-Emergent Adverse Event	xx	(xx.x%)
Number of Treatment-Emergent Adverse Events Leading to Discontinuation of Study	xx	

Note: Treatment-emergent adverse events are those events with an onset after the first application of E-BPO 5% Cream.
 Related defined as “Definitely”, “Probably”, or “Possible”. Not Related defined as “Unlikely” or “Not related”.

SOURCE: USERNAME\SPONSOR\PROJECT\JOBNAME (DATE, TIME)

Table 14.3.1.2.1: Summary of Treatment-Emergent Adverse Event Characteristics
 (Safety Population)
 (Page 2 of 2)

	E-BPO 5% Cream (N=xxx)	

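### Each change in AE intensity becomes a new entry with its own onset date and the SAP never links the entries, so event counts and by-period onsets are over-counted, and the status of some vehicle-period AEs is left undecided

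*Protocol*

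**What the plan says.** Protocol 16.2 sets the recording rule. If intensity changes over a number of days, "then separate entries should be made having distinct onset dates for the changes in severity". The rule is not limited to worsening.

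SAP 8.9.2 sets the analysis rules, all of them by onset:

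- Definition: "TEAEs are those AEs with an onset on or after the date of the first study product application".
- Entries made in this study: "For AEs recorded in the 54-07 study if the AE is not indicated as prior to first application on the CRF then it will be" classed as a TEAE.
- Carry-forward: "All AEs that were reported as ongoing in 54-01/02 will be added into the CRF for 54-07".
- Vehicle rollovers: "AEs (including ongoing) from 54-01/02 study for subjects who received vehicle in 54-01 or 54-02 will be considered pre-treatment".
- Periods: "TEAEs will be summarized in total as well as by the following periods based on time of onset in relation to date of first application" (meaning S5G4T-1), with cuts after days 85, 197 and 365.

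The same section counts a patient once per system organ class or preferred term, at the highest severity or the strongest relationship. The AE characteristics shells (Tables 14.3.1.2.1, 14.3.1.3.1, 14.3.1.4.1 and 14.3.1.5.1) also give event rows, such as "Number of Treatment-Emergent Adverse Events", overall and by period and again for serious events. A footnote to the by-period shells lets a patient into a period's denominator either by completing the period or by having an AE in it.

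**The concern.** The recording rule and the analysis rules do not fit together. The site splits one AE into several dated entries, and the analysis treats each entry as an AE in its own right. Neither document gives an episode identifier, a rule for collapsing consecutive entries, or a condition that an AE already present must worsen before it counts as treatment-emergent.

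The study exists to describe which AEs occur on long-term S5G4T-1, how severe they are and how often they occur, and the period tables carry the time dimension. Under the present text, an AE that stays mild from day 80 to day 200 is one event in the first period. An AE of the same length that fluctuates becomes several events spread over several periods. The difference comes from the bookkeeping, and it falls most heavily on long-lasting, variable AEs, which can then look like late onsets.

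**Working it through.** The documents state no figure on this point, so there is nothing to reproduce. I applied the SAP 8.9.2 rules to two invented AEs and then counted them again with the entries linked.

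**Inputs.** Period cuts from SAP 8.9.2: 0–85, 86–197, 198–365, and 366 or later. Patient A received S5G4T-1 throughout and has one continuing AE: mild from day 80, moderate from day 90, mild from day 200. Patient B came from vehicle with a moderate AE ongoing at entry, which eases to mild on day 15 after first S5G4T-1 application.

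| Entry | Onset day | Intensity | SAP as written | Linked |
|---|---|---|---|---|
| A1 | 80 | mild | TEAE, 0–12 weeks | new onset, 0–12 weeks |
| A2 | 90 | moderate | TEAE, >12–28 weeks | same AE; worsening shown in >12–28 weeks |
| A3 | 200 | mild | TEAE, >28–52 weeks | same AE; improvement, no count |
| B1 | before first application | moderate | pre-treatment | pre-treatment |
| B2 | 15 | mild | undecided: TEAE in 0–12 weeks, or pre-treatment | improvement, no TEAE |

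**Result as written.** Patient A gives 3 TEAEs and appears as an onset in three periods. Patient B gives 0 or 1, depending on which sentence is followed. The total is 3 + 0 = 3 TEAEs in 1 patient, or 3 + 1 = 4 TEAEs in 2 patients.

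**Result when linked.** 1 TEAE in 1 patient, with onset in 0–12 weeks only.

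**Why entry B2 is undecided.** The ongoing vehicle-period AE is entered in the 54-07 CRF. When it eases, Protocol 16.2 calls for a new entry dated after first application. That entry would not naturally be flagged as prior, so the sentence on 54-07 entries makes it a TEAE. The sentence on vehicle AEs, which expressly includes ongoing ones, can be read as keeping it pre-treatment. No third rule chooses between them.

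**Denominator.** If patient A left the study on day 210, A3 would still put that patient into the >28–52 week numerator. It would also put the patient into the denominator, although the period was not completed and nothing began in it.

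**Size.** If a share k of AEs has m recorded changes each, the event count is multiplied by 1 + km. Neither k nor m is in the documents, so these values are assumptions:

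- k = 5%, m = 1: 1 + 0.05 × 1 = 1.05
- k = 20%, m = 2: 1 + 0.20 × 2 = 1.40
- k = 40%, m = 2: 1 + 0.40 × 2 = 1.80

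**The case against.** The reach is narrower than it first looks. The tables by system organ class, preferred term, severity and relationship count patients, and the once-per-patient rule protects their overall versions. Patient A is one patient with that term either way. Only the event rows and the by-period tables are exposed. This stands.

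A reader might infer that the SAP definitely turns an improving vehicle-period AE into a TEAE. The documents do not support that. The sentence on ongoing vehicle AEs points the other way, and the outcome depends on how the CRF flag is set. The CRF is not among the documents and might hold a link between entries, although the SAP and its AE listing shells use none. What can be shown is a conflict between two rules.

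A reader might also infer that events are moved into later periods. They are not: the first entry keeps its period and further ones are added. Showing a later worsening in the period where it happens is useful, and a fix must not lose it.

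The number of AEs affected may be small. Protocol 15.1 and 15.2 keep dryness, scaling, itching and burning/stinging out of AE reporting unless they lead to interruption, discontinuation or new medication. AEs are elicited by a non-specific question at visits about four weeks apart, so many day-level changes may never be recorded. The study is descriptive, the error over-counts and hides nothing, and the listings give start and end dates.

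These points limit the size. They do not remove the defect, because following the stated rules gives wrong event counts and repeated onsets.

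**Conclusion.** The point holds for the event-count rows and the by-period tables. There, one AE can be counted several times and a continuing AE can be reported as an onset in more than one period.

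For vehicle rollovers it holds as an unresolved conflict within SAP 8.9.2. If the intensity-change entry is classed as a TEAE, an improving AE also raises patient-level TEAE incidence, which the once-per-patient rule cannot correct. Two programmers could reach different counts from the same data.

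Overall patient counts for AEs that began on S5G4T-1 are unaffected, provided the entries of one AE are coded to the same term.

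The size is unknown. The multipliers of 1.05 to 1.80 only show how 1 + km behaves over assumed values. They are not an estimate for this study. The point is worth settling before database lock, and the SAP preface allows updates until then.

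**What to change.** Add a linking rule to SAP 8.9.2:

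- **Linking.** In the same patient, contiguous entries of the same preferred term form one AE for event counts. Contiguous means that the next entry starts on the day the earlier one stops or the day after.
- **Incomplete stop dates.** SAP 8.1.5 imputes AE start dates only, so a rule is needed. For example, link the entries if the earlier stop date is missing or partial and compatible with the next start.
- **New onset.** Count an AE as a new onset only in the period of its first post-application onset.
- **Worsening.** In the severity-by-period tables, show a worsening in the period in which that entry starts, at that severity, labelled as worsening of a continuing AE. Giving the whole AE its first onset and its maximum severity would place late worsening in an early period and hide it.
- **Improvement.** An entry that records only improvement creates neither a TEAE nor an onset.
- **AEs that began before first S5G4T-1 application.** Count one as a TEAE only if a later linked entry is more severe than the pre-treatment severity. Use the date of that worsening as its onset for period assignment; the original onset would precede day 0 and fit no period.
- **Denominator.** State in the by-period footnote whether a new onset, a worsening, or both admit a non-completer.
- **Listing.** List the unlinked entries so the derivation can be checked.

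The cost is a short addition to the SAP, one derivation step and small changes to the shells. No new data are needed. The downside is that genuinely separate back-to-back episodes of the same term are merged. Imputed first-of-month start dates may also make some entries look contiguous when they are not; the listing of unlinked entries lets this be seen.

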16.3. Causal Relationship to Study product

The following criteria should be used in assessing the apparent causal relationship of an AE to study product:

Definitely - The AE:

- follows a reasonable temporal sequence from study product administration
- abates upon discontinuation of the study product (de-challenge)
- is confirmed by reappearance of the reaction on repeat exposure

Probably - The AE:

- follows a reasonable temporal sequence from study product administration
- abates upon discontinuation of the study product (de-challenge).
- cannot be reasonably explained by the known characteristics of the patient's state.

Possible - The AE:

- follows a reasonable temporal sequence from study product administration
- but that could readily be produced by a number of other factors.

Unlikely - The AE:

- follows a reasonable temporal sequence from study product administration.
- could have been produced by either the patient's clinical state or by study product administration.

Not related - The AE:

- does not have a reasonable temporal association with the administration of study product
- has some other obvious explanation for the event.

16.4. Eliciting and Reporting of Adverse Events

The investigator will periodically assess patients for the occurrence of adverse events. In order to avoid bias in eliciting adverse events, the patient or parent/legally authorized representative should be asked a non-specific question (e.g., "How have you been feeling since your last visit?") to assess whether any AE has been experienced since the last visit. All adverse events (as defined in [Section 16.2](#)), either observed by the Investigator or one of his/her medical collaborators, or reported by the patient spontaneously, or in response to direct questioning, will be reported and documented in the source and the study reporting forms. When reporting an adverse event, the Investigator must assign a severity grade to each event and declare an opinion on the relatedness of the event to the study product or procedure. Serious or unexpected adverse events must be reported to the CRO within 24 hours of when the Investigator first learns of the occurrence of the event.

Adverse events will be documented in the source document and recorded in a timely manner on case report forms. Adverse events that are identified at the last assessment visit (or the Early Termination Visit) must be recorded on the AE eCRF with the status of the AE noted.

Adverse event reporting begins from the signing of informed consent/assent. Study product-related adverse events should be followed until resolved or 30 days after the final study treatment. In any case, serious adverse events that are not resolved or considered to be chronic within 30 days of the final study treatment must be followed by the investigator until they become resolved or are considered to be chronic (stabilized for at least 30 days). All events that are ongoing at this time will be recorded as ongoing on the eCRF.

16.5. Expedited Reporting Responsibilities of the Study Center

For any serious or unexpected adverse event, the Sponsor or its designee must be notified within 24 hours of when the Investigator first learns of the occurrence of the event. Expedited reporting requirements for serious adverse events are described below. Adequate information must be collected with supporting documentation to complete a standard report for submission to Sol-Gel. The adverse event term on the AE eCRF and the SAE report should agree exactly. Special attention should be given to recording hospitalizations and concomitant medications.

Patients with unresolved study or product-related adverse event(s) or serious adverse event(s) should be followed by the investigator until the events are resolved, events determined to be chronic or the patient is lost to follow-up. Resolution means the patient has returned to the Baseline state of health, or the investigator does not expect any further improvement or worsening of the adverse event. The investigator should continue to report any significant follow-up information to the sponsor up to the point that the event has resolved. Any serious adverse event reported by the patient to the investigator that occurs within 30 days after the last assessment and are determined by the investigator to be reasonably associated with the use of the study product, should be reported to the sponsor within 24 hours of when the Investigator first learns of the occurrence of the event.

When reporting a serious adverse event (SAE) the Investigator (or the Study Coordinator) will promptly report any serious adverse event or pregnancy to the Sponsor or its designee by telephone email, immediately after the investigator becomes aware of the event. An SAE form should be completed and sent by fax, email, or overnight courier to the Sponsor or its designee within 24 hours of knowledge of the event by the site. In many cases, only preliminary information will be available. Appropriate follow up information should be sought (hospital discharge summaries, operative reports etc.) and a follow up SAE report form submitted. A designation of causality from the study product should always be included with a follow up report. Assess and report the causality of the event.

16.6. Submitting an Expedited Safety Report to the IRB

Once all supporting documentation is received for the reported event, the Medical Monitor, in conjunction with Sol-Gel, will determine if the safety report is eligible for expedited review. When expedited safety reporting to regulatory authorities is indeed required, the Investigator should review and update any newly available materials at once. Follow-up queries may be sent to the study center to further clarify the event.

The Sponsor, or its designee, is responsible for submitting reports of serious, unexpected related AEs to regulatory authorities on an expedited basis, according to the ICH E2A Guideline and to other regulatory authorities according to national and local regulations as required. The Sponsor, or its designee, is responsible for prompt submission to the IRB or EC of any expedited SAE reports submitted to regulatory authorities. All investigators participating in ongoing clinical studies will receive copies of the SAE reports submitted on an expedited basis to regulatory authorities

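### Protocol 16.6 makes the expedited-reporting decision wait for complete documentation, with no deadline, which conflicts with the expedited-submission duty in the same section

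*Protocol*

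**What the plan says.** Section 16.5 of the protocol sets a short clock for the site. The SAE form goes to the sponsor or its designee "within 24 hours of knowledge of the event by the site". The section accepts that this first report is often incomplete: "In many cases, only preliminary information will be available". It continues: "Appropriate follow up information should be sought (hospital discharge summaries, operative reports etc.) and a follow up SAE report form submitted". No time limit is attached to the follow-up. On causality it adds: "A designation of causality from the study product should always be included with a follow up report".

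Section 16.6 takes over once the report is with the sponsor. Its first paragraph places the expedited decision after the file is complete: "Once all supporting documentation is received for the reported event, the Medical Monitor, in conjunction with Sol-Gel, will determine" whether the report is eligible. Its second paragraph makes the sponsor or its designee responsible for "submitting reports of serious, unexpected related AEs to regulatory authorities on an expedited basis, according to the ICH E2A Guideline", and to other authorities under national and local rules. The sponsor or its designee also "is responsible for prompt submission to the IRB or EC of any expedited SAE reports submitted to regulatory authorities". Investigators in ongoing studies receive copies of the same expedited reports.

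**The concern.** The two paragraphs of 16.6 pull in different directions. The second requires speed. The first tells the people who must act quickly to wait for a full set of documents, and sets no limit on the wait. Section 16.5 makes an incomplete file at first report a common case, so the condition will matter often.

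What is at stake is how soon a serious new risk seen at one site becomes known elsewhere. The study is open-label, with approximately 700 patients at up to 56 sites (Protocol section 11), and SAP 8.1.6 plans no interim analysis or data monitoring. Under 16.6, expedited reports to regulators, to the IRB or EC and to other investigators all follow from this one decision. A delay there is passed on to all three.

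**Working it through.** No sample size, power or event count enters this point, so there is nothing to calculate. The check sets the steps from event to report in order and asks what time each one is given.

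| Step | Protocol section | Time stated |
|---|---|---|
| Site notifies sponsor or CRO of an SAE | 16.4, 16.5, 16.7 | 24 hours |
| Site sends the SAE form | 16.5 | 24 hours |
| Site obtains and sends follow-up documents | 16.5 | None |
| Medical Monitor and sponsor decide on expedited handling | 16.6, first paragraph | None; conditional on all supporting documentation |
| Sponsor submits to regulators | 16.6, second paragraph | Expedited, by reference to ICH E2A and national and local regulations; no day count in the protocol |
| Sponsor submits to IRB or EC | 16.6, second paragraph | Prompt, for reports already sent to regulators |
| Other investigators receive copies | 16.6, second paragraph | None; same reports |

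Section 16.8 adds a one-working-day limit for pregnancy outcomes classed as SAEs. That also runs from site to sponsor.

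Three things follow.

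1. *The gap is at the sponsor.* Every numeric limit on an initial SAE report ends when the sponsor, its designee or the CRO is told. From there to the expedited decision, no number of hours or days is stated.

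2. *The decision covers regulatory reporting, not IRB handling alone.* The title of 16.6 mentions only the IRB, and its first sentence speaks of eligibility for expedited review. But the next sentence deals with the case where expedited reporting to regulatory authorities turns out to be required. The paragraph is therefore the gate for the duty in the paragraph below it.

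3. *The condition can be slow to meet.* Section 16.2 makes in-patient hospitalization an SAE criterion, and 16.5 names discharge summaries among the documents to be sought. If those count as supporting documentation, the condition cannot be met while the patient is still in hospital. If they do not, the text still says that everything must be received first, and does not say what everything is.

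Causality needs a separate check, because expedited submission applies to related events. Section 16.4 obliges the investigator to give an opinion on relatedness when reporting any adverse event, which includes SAEs. In 16.5 the sentence directly after "A designation of causality from the study product should always be included with a follow up report" is a general instruction to assess and report causality, not confined to follow-up. The requirement at first report therefore exists. What is missing is only that 16.5, the section a site would consult when completing the form, says always for the follow-up report and does not repeat the 16.4 requirement for the initial one.

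**The case against.** The best defence is that the submission duty has an outside limit. The second paragraph of 16.6 binds the sponsor to ICH E2A and to national and local regulations, and section 9 commits the study to FDA regulations and ICH GCP. Every SAE, related or not, reaches the sponsor within 24 hours under 16.7, and a Medical Monitor assesses it. This stands as far as it goes. A reader might infer that a report can wait without limit, or that expedited submission becomes impossible. The documents do not support either: the decision step has no clock of its own, but the duty it serves is tied to external rules. Their day counts are not in the documents and are not relied on here. The defence does not remove the conflict, because an instruction to wait for all documents still works against the duty it feeds.

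A second defence is one of terms. Section 16.5 uses supporting documentation for what completes the standard report to the sponsor, and follow-up information for discharge summaries and operative reports. Section 16.6 uses the first term and then provides for newly available materials and follow-up queries, which suggests that information was expected to keep arriving. This makes the text ambiguous, and the authors may not have meant the strict reading. The requirement that all such documentation be in hand before the decision remains on either reading.

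A third concerns causality. A reader of 16.5 alone might infer that it is required only in a follow-up report. Section 16.4 and the next sentence of 16.5 rule that out. The separate SAE and pregnancy form instructions cited in 16.7, which are not among the documents, may also cover the initial form.

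**Conclusion.** The point holds as a conflict of sequencing within 16.6, and between 16.6 and 16.5. The expedited decision is placed after receipt of all supporting documentation, with no deadline, while the same section requires expedited submission and 16.5 expects first information to be preliminary. It should be corrected, since following the text as written can delay safety reports to regulators, the IRB or EC and other investigators. It affects no treatment, endpoint or analysis.

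Its size is one step in the reporting chain without a stated time. A length of delay cannot be given, because the documents do not say how long supporting documents take to arrive. A reader might try to size the matter by multiplying patients by daily applications over some assumed delay. That is not supportable: the delay would be invented, approximately 700 is planned enrolment and not the number on product at once, and 14.1 withholds product from anyone rated clear or almost clear.

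The conclusion assumes that staff follow 16.6 in the order written and that no safety procedure outside the two documents overrides it. The causality wording is a minor alignment only.

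**What to change.** Replace the first sentence of 16.6 with wording such as: *On receipt of the initial SAE report, and on the information then available, the Medical Monitor and the sponsor determine whether expedited reporting applies; the decision is reviewed as further documentation arrives.* The second paragraph can stay as it is.

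As a smaller alignment, add to 16.5 that the relatedness opinion already required by 16.4 is given on the initial SAE form and on each follow-up form.

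This costs two sentences of protocol text. The downside is that some decisions will rest on partial information, so a few early reports may later be downgraded.
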